Population:	Patients with T2DM (ages 30-75, all sexes). We will plan to consent 50 participants with the goal of randomizing 42 and having 35 subjects complete the study.
Intervention:	Dapagliflozin 10mg/day and Placebo each for 6 weeks in a cross-over design
Objectives:	
 1. To assess the impact of dapagliflozin on EC health in patients with T2DM 2. To assess the impact of dapagliflozin on vasodilator function and additional measures of vascular health including arterial stiffness and markers of inflammation
Design/Methodology:	The overall study design is a two-treatment, two-period cross-over study. Subjects will be randomized to treatment order in a 1:1 ratio to receive SGLT2 inhibitor (dapagliflozin) and then placebo or vice versa in a cross-over design. Total study period for each study subject is 14 weeks consisting of: two treatment periods (dapagliflozin and placebo) lasting 6 weeks each (12 weeks total) and a 2 week washout period between treatment periods. Each subject undergoes a washout period of 2 weeks after completing first 6 weeks of treatment with either placebo or dapagliflozin. This is followed by cross-over to the alternate treatment for a period of 6 weeks with dapagliflozin or placebo depending on their first

	treatment. Randomization will be done in block sizes of 2 or 4. Once assigned to treatment, participants will receive dapagliflozin 10 mg/day or placebo for 6 weeks. A detailed schedule of events is in the appendix.
Endpoints	Primary endpoint: EC health measured as response to insulin Secondary endpoint: Endothelial vasodilator function measured flow-mediated dilation of brachial artery Other Secondary Endpoints: vascular health measures, arterial stiffness, EC RNA, circulating biomarkers of vascular health
Total Study Duration:	We estimate that the study will last four years from IRB approval through data analysis.
Subject Participation Duration:	Total of 14 weeks after starting study intervention
Key Procedures:	1 screening visit, 4 study visits, 2 study phone calls.

3 Background/Rationale & Purpose

3.1 Background Information

Type 2 Diabetes Mellitus (T2DM) is a key public health problem worldwide with current trends predicting that 500 million people will have diabetes in 2035.¹ The escalating prevalence of T2DM worldwide presents a critical cardiovascular (CV) challenge.^{2,3} Patients with T2DM experience accelerated vascular aging, premature atherosclerotic CV disease, and increased rates of CV events.^{4,5} There is considerable interest in the clinical CV benefits of new agents to treat T2DM including SGLT2 inhibitors such as dapagliflozin.^{6,7} However, the mechanisms of that drive the cardiovascular health benefits of dapagliflozin remains incompletely understood.

Metabolic disturbances underlie the systemic vascular dysfunction in T2DM. Elevated glucose and lipids alter signal transduction thereby changing gene expression resulting disturbing endothelial homeostasis.⁸ Alterations in endothelial function including inflammation and reduced nitric oxide (NO) production promote atherogenesis in T2DM.⁹

Several studies suggest activity of SGLT2 inhibitors on vascular function in animal models and humans.¹⁰⁻¹² Dapagliflozin has effects on endothelial inflammation in cultured cells and improved vasodilation in animal models¹³; however the effect on EC health in patients is not well-defined. Emerging experimental evidence in preclinical models also links SGLT2 inhibitors to reduction in mitochondrial oxidative stress¹⁴. Our study will provide novel evidence about EC effects of dapagliflozin that link to both animal models of T2DM and clinical trial data.

This study will be conducted in compliance with the protocol, applicable regulatory requirements, and Boston Medical Center/Boston University Medical Campus Human Research Protection policies and procedures.

3.2 Rationale and Purpose

There is considerable interest in the clinical CV benefits of new diabetes medications including dapagliflozin (SGLT2 inhibitor).^{6,7} However, the mechanisms that underlie the CV benefits remain incompletely defined. The robust clinical trial evidence with SGLT inhibitors has not yet been

accompanied by complete mechanistic evidence in the vasculature. Combining vascular functional assessment with targeted EC gene expression and NO characterization will expand critical evidence about the mechanisms of action. Prior clinical studies evaluating the effects of SGLT2 inhibitors have been limited to evaluation of vascular health without measures of EC phenotype that will provide additional mechanistic information. Dapagliflozin has effects on endothelial inflammation in cultured cells and improved vasodilation in animal models¹³; however, the effect on EC health in patients is not well-defined. Emerging experimental evidence in preclinical models also links SGLT2 inhibitors to reduction in mitochondrial oxidative stress¹⁴.

We propose to investigate treatment with novel medications (SGLT2 inhibitor) for T2DM will alter endothelial phenotype and ncRNA or biomarkers. We plan to test this hypothesis by conducting an interventional cross-over study with dapagliflozin (SGLT2 inhibitor). We anticipate that evaluating EC phenotype will provide key additional information regarding the ability of novel treatments for T2DM to restore vascular health.

4 Objectives

4.1 Study Objectives

The overarching objective of this mechanistic study is to learn how an SGT2 inhibitor, dapagliflozin, impacts vascular health in patients with T2DM. We aim to compare the changes in vascular health to changes in EC phenotype including ncRNA to develop evidence supporting the mechanism of cardiovascular benefit of SGLT2 inhibitors. This study will provide novel information regarding the mechanism of effects of novel treatments for endothelial function and vascular health in patients with T2DM to reduce CV risk.

1. To assess the effects of dapagliflozin on EC phenotype.
2. To assess the impact of dapagliflozin on vasodilator function and additional measures of vascular health including arterial stiffness and circulating markers of vascular health.

4.2 Study Outcome Measures.

4.2.1 Primary Outcome Measures

The primary outcome is insulin-mediated eNOS phosphorylation measured in ECs. The percentage change in the phosphorylation of eNOS is measured using quantitative immunofluorescence microscopy in EC collected before and after each treatment period.

4.2.2 Secondary Outcome Measures

Key Secondary Outcome: Flow-mediated dilation of the brachial artery measured by ultrasound. We measure the percentage change in the diameter of the brachial artery before and after a 5 minute cuff occlusion on the arm as a measure of endothelial function. We will measure before and after each treatment period.

Other secondary Endpoints:

- Arterial stiffness measured by tonometry
- Microvascular dilator function by EndoPAT
- Plasma measures of noncoding RNA
- EC measures of noncoding RNA
- EC measures of coding RNA
- Circulating biomarkers of vascular health including BNP and CRP
- Fasting glucose, insulin, and lipid profile
- Body weight and waist circumference

5 Study Design

5.1 Overall design:

The overall design is a single center randomized, double-blind, cross-over, placebo-controlled study of dapagliflozin (an SGLT2 inhibitor) compared to placebo in patients with T2DM. Each treatment period lasts 6 weeks with a 2 week washout period between study treatments. The study intervention is 10mg per day of dapagliflozin compared to placebo. Vascular health measures including EC, vasodilator function, and circulating biomarkers will be measured before and after each treatment period. An outline of the study visits and procedures is in the appendix. A cross-over design is being used in order to be able to be able to minimize variability by comparing within individual effects. Prior studies from our group and others have not shown carry-over effects with regards to the primary outcome measures.

Subjects will be randomized 1:1 ratio to receive SGLT2 inhibitor (dapagliflozin 10mg/day) and then placebo or vice versa. Treatment order will be block randomized in block sizes of 2 or 4. 50 subjects will be consented with the goal of randomizing 42 and having 35 study completers.

Participants will be adult men and women who are outpatients with established T2DM. All participants will receive both study interventions.

The study intervention is an FDA-approved medication used in the FDA-approved study population with the objective of identifying mechanisms of cardiovascular health effects thus the study does not fit into an FDA defined trial Phase.

The study is a single site study and all procedures will be conducted at Boston University using established methodology in [name] laboratory. Clinical laboratory tests will be conducted in Boston Medical Center pathology. All data will be managed by BEDAC in a centralized manner using established quality control protocols.

6 Potential Risks and Benefits

6.1 Risks

Blood collection: will cause momentary discomfort and is associated with a very small risk of bruising or infection. There is a slight chance that a bruise or infection will develop at the puncture site.

Insertion of the J wire: there is the small possibility that a bruise or infection will develop at the puncture site. There is a very low chance that the J-wire could break during the procedure that could require a procedure to remove the part of the wire from your body. None of these are common occurrences. None of these have occurred in the more than 2500 times the procedure has been performed at BUMC. The procedure will be performed by a trained physician or nurse.

During inflation of the blood pressure cuff for 5 minutes, there will be tightness and numbness in the arm and hand that will pass within a few seconds after cuff release.

The nitroglycerin may cause a headache or hypotension lasting for up to 30 minutes. It will be given under the supervision of a physician while the subject is lying down. We measure blood pressure as part of the study, and the nitroglycerin portion of the study will be omitted if systolic blood pressure is less than 100 mmHg. Prior to nitroglycerin administration, we will ask the subject about history of migraine headaches, prior nitroglycerin use, and the use of Viagra®, Cialis®, or Levitra®. The nitroglycerin could cause a serious drop in blood pressure if taking any of these drugs. If the participant has taken any of these drugs within a week of any study visit they will still be eligible for the study, but the nitroglycerin portion of the vascular function testing will be omitted.

The study intervention: Potential Adverse Effects of dapagliflozin: (Please see attached package insert for additional information)¹⁵.

- Hypoglycemia: There is a low risk of hypoglycemia even when dapagliflozin is combined with other common oral anti-diabetes medications. In the DECLARE-TIMI 58 study, there was a lower rate of a major hypoglycemic event (0.7%) in the dapagliflozin compared to the placebo group (1.0%)¹⁶. A meta-analysis that included 14 RCTs comparing the effects of dapagliflozin 10mg against placebo did not find a difference in the risk of hypoglycemic events (HR 0.97, CI 0.82-1.15)¹⁷. Another meta-analysis that included 15 RCTs compared dapagliflozin in conjunction with other diabetes medications metformin, insulin, or GLP1-agonist exenatide versus placebo plus these medications also showed no increased risk of hypoglycemia (RR 1.04, CI 0.93-1.17)¹⁸. The drug manufacturer recommends cautious use in patients taking insulin secretagogues (e.g. sulfonylureas) and insulin, which themselves carry a risk of hypoglycemia due to their mechanism of action^{15, 19}. Taken together, these data suggest that the risk of hypoglycemia from dapagliflozin is only present when taken in conjunction with insulin or sulfonylureas, but not other commonly prescribed anti-diabetes medications metformin or GLP1-agonists. We will exclude participants with history of major hypoglycemic events in the past 6 months and/or HbA1c<6.5%. For patients on either insulin or sulfonylurea therapy we will consult with the patient's diabetologist to titrate diabetes medications appropriately to minimize risk of hypoglycemia.
- Volume depletion: Dapagliflozin has a mild diuretic effect. The rate of symptoms of volume depletion in DECLARE-TIMI 58 was similar in the dapagliflozin compared to the placebo group. We will exclude individuals with systolic blood pressure less than 100mmHg

- Genital mycotic infections: there is a small risk of genital mycotic infections (0.9%). We will exclude participants with a history of more than one genital mycotic infection in the past two years.
- Hypersensitivity reaction: There is a low rate (0.4%) of hypersensitivity including rash or angioedema. Patients with history of allergy to SGLT2 inhibitors will be excluded.
- Bladder cancer: there is a very low rate of association with bladder cancer. Patients with a history of bladder cancer or a history of radiation therapy to the lower abdomen or pelvis will be excluded.
- Urinary tract infection: there is a small increase in the rate of urinary tract infection. We will exclude participants with a history of chronic cystitis and/or recurrent urinary tract infections (3 or more in the last year).
- Nausea (1-10%)
- Low rate of serious infections in the penis or vagina including necrotizing fasciitis of the peroneum.
- May increase LDL cholesterol level
- Dizziness or headache (1-10%)
- Low rate of ketoacidosis.

Protection of confidentiality: All samples and data files will be de-identified and coded. All paper files will be stored in locked cabinets and electronic files will be password protected. The studies will be opened to all participants regardless of sex or race/ethnicity. The participant voluntary recruited will be asked to provide consent before being included in the study.

Pregnancy during the study: If patients get pregnant while in this study, it could be bad for the fetus/baby. As described in the package insert, there is animal data suggesting adverse renal effects in the second and third trimesters of pregnancy. Limited data with dapagliflozin in pregnancy women are not sufficient to determine drug-associated risk for major birth defects or miscarriage. In order to mitigate this risk, we will complete a blood pregnancy test prior to the first visit to mitigate for this risk and collect information regarding use of birth control. If the subject is of child-bearing potential, she must use birth control if she is a woman having sex with men while in this study. She should also keep using birth control for three months after the study ends. Only some birth control methods work well enough to be safe while enrolled in this study. These methods are oral contraceptives (the pill), intrauterine devices (IUDs), contraceptive implants under the skin, contraceptive rings or patches or injections, diaphragms with spermicide, and condoms with foam. Subject should not be in this study if she is a woman who has sex with men and cannot use one of these birth control methods.

The investigators will continuously monitor subjects for adverse events by asking about such events at follow up phone call and study visit and by instructing the subjects to contact the investigators immediately if they experience unexpected problems. Investigators will call the participants by phone call two times (once during each treatment period) and will discuss adverse effects or change in medical status, and assess subject compliance. In addition, the principal investigator will monitor the literature for reports and studies of the clinical use SGLT2 inhibitors for new information on additional risks.

If there is any study related unexpected event, problems with recruiting, or new information derived from the literature, the principal investigator will review the situation, consult with co-investigators and decide about modifying the protocol or stopping the study.

There may be unknown risks or discomforts involved.

6.2 Potential Benefits

The study will provide novel information regarding vascular function in patients with T2DM who undergo treatment with SGLT2 inhibitors. CV disease is the leading cause of death and disability in this country and costs billions of dollars each year. The findings may be relevant to the management of CV disease. The results of these studies have the potential to be the foundation of novel therapeutic development for patients with T2DM to reduce CV risk.

6.3 Analysis of Risks in Relation to Benefits

In the opinion of the investigators, the potential benefits (understanding the mechanism of benefit of SGLT2 inhibitor treatment for T2DM for CV disease that could lead to improved outcomes) far outweigh the risks associated with this study (non-invasive testing of vascular function, blood collection, measuring endothelial function).

7 Study Subject Selection

7.1 Subject Inclusion Criteria

In order to be eligible to participate in this study, an individual must meet all of the following criteria:

1. Male and Female subjects.
2. Age 30-75 years old
3. Diagnosis of T2DM for minimum of 3 months
4. BMI>25
5. Willing to give informed consent and able to understand, to participate in and to comply with the study requirements.

7.2 Subject Exclusion Criteria

An individual who meets any of the following criteria will be excluded from participation in this study:

1. Treatment with anticoagulation within last 30 days
2. Treatment with SGLT2 inhibitor within the last 60 days
3. HbA1c>9.5% within last 3 months timeframe
4. Systolic blood pressure less than 100mmHg
5. History of genital mycotic infections: more than one genital mycotic infection in the past two years.

6. History of recurrent urinary tract infections: history of chronic cystitis and/or recurrent urinary tract infections (3 or more in the last year).
7. History of allergy to SGLT2 inhibitor
8. History of bladder cancer or prior pelvic radiation
9. We will exclude participants with more than one hypoglycemic events in the past 6 months and/or HbA1c<6.5%. For patients on either insulin or sulfonylurea therapy we will consult with the patient's diabetologist to titrate diabetes medications appropriately to minimize risk of hypoglycemia.
10. Women who are lactating or pregnant. All women with childbearing potential will undergo a blood pregnancy test at baseline visit to exclude pregnancy and be required to use birth control throughout the study period.
11. Treatment with an investigational product within the last 30 days.
12. Clinically evident major illness of other organ systems, including clinically evident cancer, end-stage renal failure or other conditions that in the opinion of the principal investigator make this clinical study inappropriate.

8 Study Intervention

The study intervention will involve the use of an SGLT2 inhibitor dapagliflozin

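### The operative hypoglycemia exclusion (7.2, criterion 9) passes a patient with one recent major event, whom section 6.1 says is excluded

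*Combined protocol and SAP*

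**What the plan says.** Section 6.1 (Risks) discusses hypoglycemia as a risk of the study drug and gives an exclusion as part of the mitigation: "We will exclude participants with history of major hypoglycemic events in the past 6 months and/or HbA1c<6.5"%. It sets no number of events and restricts the rule to major ones.

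Section 7.2 (Subject Exclusion Criteria), criterion 9, reads: "We will exclude participants with more than one hypoglycemic events in the past 6 months and/or HbA1c<6.5"%. It sets a number, two or more, and has no severity qualifier.

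The 6-month window, the HbA1c floor, and the instruction to consult the diabetologist and adjust therapy for insulin or sulfonylurea users are the same in both places. Under 7.2, meeting any one listed criterion excludes the patient. Section 9 (Recruitment) has the coordinator screen records against the inclusion and exclusion criteria.

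**The concern.** Section 6.1 presents the exclusion as a safeguard against a named drug risk, but the safeguard applied at screening is a different one. One rule turns on severity and the other on count, so a patient whose only event in the window was a major one can pass the list that decides eligibility.

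Under section 5.1 every participant is to receive both treatments, so anyone admitted this way is due to take dapagliflozin. Insulin and sulfonylurea users are eligible, and they are the group of whom 6.1 says that "the risk of hypoglycemia from dapagliflozin is only present when taken in conjunction with insulin or sulfonylureas". What is at stake is patient safety and consistent eligibility decisions. The statistical analysis is not touched.

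**Working it through.** No sample size, power or alpha figure bears on this point, so the check is a comparison of the two rules, followed by a rough size.

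**Step 1: apply both rules to the possible histories.** Take a patient with HbA1c between 6.5% and 9.5%, so that neither HbA1c exclusion applies, and count events in the past 6 months. Read 6.1 as covering any major event.

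| History | Section 6.1 | Criterion 9 |
|---|---|---|
| One major, no other | Excluded | Not excluded |
| One major plus one or more minor | Excluded | Excluded |
| Two or more major | Excluded | Excluded |
| One minor, no other | Not excluded | Not excluded |
| Two or more minor, none major | Not excluded | Excluded |

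The rules disagree in the first and last rows. The first is the safety gap. In the last, 7.2 is the more protective text.

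**Step 2: is any major event the right reading of 6.1?** Where 6.1 wants a threshold it gives one. For genital infection it says "We will exclude participants with a history of more than one genital mycotic infection in the past two years", and for urinary infection it requires three or more in a year. Criteria 5 and 6 carry both thresholds over unchanged. The hypoglycemia sentence has no threshold, so the natural reading is any major event.

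**Step 3: what else would stop a patient with a single major event?**

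- Criterion 12 covers "other conditions that in the opinion of the principal investigator make this clinical study inappropriate". It is discretionary and does not name hypoglycemia.
- Provider agreement is described in section 9 for clinic recruitment, but not for people who respond to an advertisement.
- At the screening visit (section 9) investigators review every consented patient's medical history again. The purpose is to confirm eligibility, and this patient meets criterion 9 as written.
- Adjustment of diabetes therapy applies only to insulin or sulfonylurea users and does not exclude anyone.
- The HbA1c floor does not reach a patient at 6.5% to 9.5%.

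**Step 4: rough size.** The documents give no frequency for this history. The nearest figures are the major-event rates that 6.1 cites from a large outcome trial, 0.7% on dapagliflozin and 1.0% on placebo. They are on-trial rates, not a 6-month history in this population. Take an assumed prevalence p of 0.5% to 1% and n = 42 randomized (section 12.2). The expected number is 42p, and the chance of at least one is 1 − (1 − p)^42.

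- p = 0.005: 42 × 0.005 = 0.21; 1 − 0.995^42 = 0.190
- p = 0.007: 42 × 0.007 = 0.29; 1 − 0.993^42 = 0.255
- p = 0.010: 42 × 0.010 = 0.42; 1 − 0.990^42 = 0.344

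These are chances of randomizing such a patient, not of harm.

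**The case against.** The strongest reply is that 6.1 uses the plural, events. Read as two or more major events, 6.1 is the narrower rule, criterion 9 covers everyone it excludes, and the safety gap disappears. That reading is possible but less natural, because 6.1 states counts elsewhere. Even then the sections still conflict, since only one is limited to major events.

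A second reply is that investigators see every participant's history at screening, on both recruitment routes, and that 6.1 is itself current protocol text they could follow. This stands in part. It puts the history before someone who can invoke criterion 12, and it weakens any contrast between clinic and advertisement recruits. But it leaves the outcome to judgment, with two texts that disagree.

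A third reply is that the evidence cited in 6.1 is reassuring. The major-event rate in the outcome trial was lower on dapagliflozin than on placebo, and two meta-analyses found no increase (HR 0.97, 0.82 to 1.15; RR 1.04, 0.93 to 1.17). Insulin and sulfonylurea users also have their therapy reviewed. This limits the likely consequence, but it does not explain why the stated safeguard differs from the applied one.

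Finally, the prevalence range is weakly anchored: its lower end matches no figure in the documents, and the true value could lie outside it in either direction. That is fair. The percentages show only that the number is likely to be small.

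**Conclusion.** The concern holds. Criterion 9 as written admits a patient with exactly one major hypoglycemic event and no other event in the past 6 months, and 6.1, on its natural reading, says that patient is excluded. That the two rules differ is certain on any reading; the direction of the safety gap rests on taking 6.1 to mean any major event.

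The gap is one narrow history. Under the assumed 0.5% to 1% prevalence, fewer than one such patient is expected among 42, with roughly a one-in-five to one-in-three chance of at least one. The HbA1c floor, therapy adjustment and investigator discretion reduce the consequence further. This should be corrected because it concerns safety and costs little. It does not affect power, alpha or the analysis model.

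**What to change.** Amend criterion 9 to exclude patients with any major hypoglycemic event in the past 6 months, with major defined in the criterion, or more than one hypoglycemic event of any severity in that period, and/or HbA1c below 6.5%. Use the same wording in 6.1. This keeps every protection that either section now gives. If the sponsor intended a narrower rule, it should choose one and state it identically in both places.

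The cost is a short wording amendment. Relative to the present criterion 9, the combined rule newly excludes only patients with a single major event. At the assumed prevalence that is 50 × 0.005 = 0.25 to 50 × 0.01 = 0.5 of the 50 patients to be consented, so at most a rare extra screen failure.

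The same amendment can settle a separate mismatch of the same kind. Section 6.1 says that patients with "a history of radiation therapy to the lower abdomen or pelvis will be excluded", while criterion 8 lists only "History of bladder cancer or prior pelvic radiation" and so omits the lower abdomen.

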8.2 Dosing

Subjects randomized to the dapagliflozin-then-placebo arm, will be instructed to administer dapagliflozin 10mg once daily for 6 weeks. Week 7 & 8 will be provided as a washout period. Afterwards, subjects will receive the placebo 0mg once daily for the remainder 6 weeks. The dose has been selected based on prior studies demonstrating the impact on cardiovascular health at the dose of 10mg and the safety profile is well-established with starting at the 10mg dose from multiple studies both including individuals with and without Type 2 diabetes with an acceptable safety profile.

Subjects randomized to the placebo-then-dapagliflozin arm, will be instructed to administer placebo 0mg once daily for 6 weeks. Week 7 & 8 will be provided as a washout period. Afterwards, subjects will receive the dapagliflozin 10mg once daily for the remainder 6 weeks.

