Randomization: The study statistician at BEDAC will supervise computer generation of the randomization scheme. Randomization scheme will be provided to the IPS team in a blinded manner. Investigators and other team members will not have access to the randomization table. Un-Blinding will occur when all subjects have completed treatment and evaluation of the primary outcome data measures is complete. Un-blinding must be requested by the PI.

Treatment Period: Subjects will be randomized (1:1) to receive dapagliflozin and then placebo or vice versa. Total treatment period when participants are taking medication (either placebo or dapagliflozin) is 12 weeks consisting of 6 weeks of treatment for each dapagliflozin and placebo with 2 weeks of washout period in between. Subjects randomized to dapagliflozin will receive 10 mg/day (in capsule form). Subjects randomized to placebo will receive matching placebo capsule. Treatment order will be block randomized in block sizes of 2 or 4. We will call patients to ascertain compliance at week 3 into each treatment.

Treatment Plan:

The Boston Medical Center Investigational Drug Service will dispense 6 weeks supply of either dapagliflozin or placebo depending on their randomized group. Subjects will be instructed to contact the investigators if they experience adverse events or a change in healthy status.

Study Telephone Call 1: Subjects will be contacted in the 3rd week of the treatment period to evaluate self-reported compliance, assess for any relevant side effects, adverse events and change in clinical status.

Study Visit 2:

After arrival in the research unit, the investigators will perform a pill count to assess subject compliance, and complete an assessment of side effects and any change in clinical status. We will then perform all the study procedures to evaluate vascular health as described from Study Visit 1.

Study Visit 3:

After a washout period of 2 weeks (participants instructed not to take research medications during this time), patients will return to start treatment with either dapagliflozin or placebo for 6 weeks. We will perform all the study procedures from Study Visit 1. When assigned to dapagliflozin, participants will receive 10 mg/day (in capsule form) for the period of treatment. Subjects assigned to placebo will receive matching placebo capsules.

Telephone Call 2: We will call patients at week 3 as described for telephone Call 1.

Study Visit 4:

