
15 Appendix

Schedule of Events

Visit number	Screening	Visit1	Phone call	Visit2		Visit3	Phone call	Visit4
Study week	Up to -4	0	3	6		8	11	14
Eligibility	x							
Demographics & Medical History	x							
HbA1c with 3 months	x							
Assessment of Inclusion/Exclusion criteria	x							
Pregnancy test for women of childbearing potential	x							
In person consent	x							
Medication history	x	x	x	x		x	x	x
Weight, height, waist circumference	x	x		x		x		x
Randomization		x						
Vascular function, BP, HR, arterial stiffness		x		x		x		x
Lipids, Glucose		x		x		x		x
Plasma, biomarkers, miRNA		x		x		x		x
Endothelial cell phenotype		x		x		x		x
Endothelial Cell RNA		x		x		x		x
Dispense Study drug		x				x		
Assess Compliance			x	x			x	x
		Dapagliflozin 10mg/day or placebo	Dapagliflozin 10mg/day or placebo	Dapagliflozin 10mg/day or placebo		Dapagliflozin 10mg/day or placebo	Dapagliflozin 10mg/day or placebo	Dapagliflozin 10mg/day or placebo
Symptom Assessment		x	x	x		x	x	x

Schematic of Study Design

Figure 10. Study Overview.

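### The only pregnancy test is at screening, so women of child-bearing potential in the placebo-first sequence start dapagliflozin at Visit 3, 8 to 12 weeks after it

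*Combined protocol and SAP*

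**What the plan says.** Criterion 10 in Section 7.2 excludes pregnant or lactating women and states that women of child-bearing potential "will undergo a blood pregnancy test at baseline visit to exclude pregnancy and be required to use birth control throughout the study period". Section 6.1 places the blood test before the first visit. Section 9 (Screening Visit) places it at screening, and offers a combined screening and Visit 1 day only to people who are not of child-bearing potential.

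In the Schedule of Events (Section 15), the row "Pregnancy test for women of childbearing potential" has a single mark, under Screening. The row "Dispense Study drug" has two, at Visit 1 (week 0) and Visit 3 (week 8).

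For the placebo-first arm, Section 8.2 describes 6 weeks of placebo and a 2-week washout, and continues: "Afterwards, subjects will receive the dapagliflozin 10mg once daily for the remainder 6 weeks". Section 9 says of Visit 3: "We will perform all the study procedures from Study Visit 1". The Visit 1 list covers vital signs, blood collection, vascular function, arterial stiffness, endothelial cell collection, biochemistry and stored samples. It has no pregnancy test.

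Other safeguards are written in:
- Section 6.1 requires contraception from a list of accepted methods during the study and for three months afterwards, and collects information on its use.
- The schedule marks "Medication history" at all seven later contacts or screening, and "Symptom Assessment" at six.
- At Visits 2 and 4 the investigators "complete an assessment of side effects and any change in clinical status".
- Sections 6.1, 9 (Treatment Plan) and 10.2 tell participants how to report problems or changes in health between contacts.

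**The concern.** Section 6.1 does not rely on contraception alone. It adds a blood test expressly to reduce the risk of exposing a pregnancy, noting adverse renal findings in animals and insufficient human data. A test does that job only if it is close to the start of active treatment.

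In a two-period crossover, active treatment starts at two different times. One test at entry serves the sequence that begins with dapagliflozin. For the other sequence, the first active capsule comes after a full placebo period and a washout, and nothing in the plan verifies pregnancy status in between. A pregnancy that began in that interval and was not recognised or reported would be exposed to dapagliflozin even though the plan had been followed exactly. The withdrawal rules in Sections 8.5 and 9 also do not name pregnancy, so the plan does not spell out what follows a positive result.

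**Working it through.** This is calendar arithmetic; no power or error-rate calculation is involved.

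**Inputs**
- Week of the only test: s, between -4 and 0 (Section 9, Screening Visit; Schedule of Events).
- Period 1: 6 weeks; washout: 2 weeks; period 2: 6 weeks (Section 8.2).
- Number randomized: 42, allocated 1:1 (Section 5.1).

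**Reproducing the schedule**
- Visit 3 = 6 + 2 = week 8.
- Visit 4 = 8 + 6 = week 14.
- Both agree with the Schedule of Events.

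**Weeks from the only test to dapagliflozin**

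| Sequence | First capsule | Last capsule |
|---|---|---|
| Placebo-first | 8 - s = 8 to 12 | 14 - s = 14 to 18 |
| Dapagliflozin-first | 0 - s = 0 to 4 | 6 - s = 6 to 10 |
| Placebo-first, with a test at Visit 3 | 8 - 8 = 0 | 14 - 8 = 6 |

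Whatever the value of s, the placebo-first gap is 8 weeks longer than the dapagliflozin-first gap.

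**Which end of the range applies.** Exactly 8 weeks requires the test to be on the day of Visit 1, which holds only if the baseline visit in criterion 10 means Visit 1. Section 6.1 puts the test before the first visit, and Section 9 gives women of child-bearing potential a separate screening visit, so the usual gap should exceed 8 weeks. The protocol states no visit windows; a late Visit 3 would lengthen it further.

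**Does the Visit 3 wording supply a test?** No. It repeats the Visit 1 procedures, and neither the Visit 1 text in Section 9 nor the Visit 1 column of the schedule contains a pregnancy test.

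**How many people.** 42 / 2 = 21 participants are expected in the placebo-first sequence. They are of all sexes and aged 30 to 75, so women of child-bearing potential are only a part of the 21. The documents give no figure for that part.

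**The case against.** The plan has a coherent strategy: a blood test at entry, mandatory contraception from a closed list, and no participation for a woman who has sex with men and cannot use a listed method. Nothing in the documents promises or requires a repeat test. The symptom and status checks at week 3, week 6 and week 8 all come before or at the second dispensing, and the standing instructions cover the time between them. All of this stands, and it keeps the point small. What remains is that each of these safeguards depends on the woman noticing and reporting, whereas before period 1 the plan adds a test.

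A reader might infer more: that the design exposes pregnancies in the second trimester, where Section 6.1 places the animal findings. The documents do not support that as an expected outcome. Assume usual dating, with gestation equal to weeks since conception plus 2 and the second trimester from week 14. A placebo-first conception at study week c reaches 14 - c + 2 = 16 - c weeks by the last capsule, so only conceptions up to week 2 reach 14. A conception at week 2 does so only as dosing ends. One at week 0 runs from 10 to 16 weeks during dapagliflozin, so only the last 2 weeks count. The extreme of 14 to 20 weeks needs both test and conception at week -4. Each case also needs contraceptive failure and a pregnancy still unrecognised or unreported at Visit 3, when it would be at least 8 - 2 = 6 weeks from conception. The scenario is possible but narrow.

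Two practical objections also stand. A Visit 3 result comes after randomization, so it cannot be part of an entry criterion. And no laboratory turnaround time is stated, so a blood result on the day cannot be assumed.

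**Conclusion.** The point holds as a modest gap in safety procedures. As written, pregnancy status is verified 0 to 4 weeks before first active exposure in one sequence and 8 to 12 weeks before it in the other. This rests on the schedule's single mark for the test, dispensing at week 8, and visits kept to their nominal weeks.

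It should not be read as showing that the plan breaches a requirement or that an exposed pregnancy is likely. The documents cite no rule for repeat testing, very few women are affected, and no case count can be derived. No endpoint, analysis or sample size is affected. The reason to act is the potential harm that the protocol itself describes, set against a small cost. It is a desirable improvement, not a condition for the trial to proceed.

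**What to change.** Add a pregnancy test at Visit 3 for all women of child-bearing potential in both sequences, and require a negative result before period 2 capsules are dispensed. Testing both sequences keeps the blind.

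Text to change:
- Section 9, Study Visit 3: add the test and the condition for dispensing.
- Section 15, Schedule of Events: add a mark under Visit 3 in the pregnancy test row.
- Section 6.1: mention the second test beside the one before the first visit.
- Sections 8.5 and 9 (Earlier termination): add a positive pregnancy test to the reasons for withdrawal.
- Section 7.2, criterion 10: keep it as an entry criterion, but name the screening visit instead of the baseline visit, so that it agrees with the schedule and the screening text.

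The cost is one extra assay for each woman of child-bearing potential who reaches Visit 3. Blood is already drawn at that visit. If a blood test is used, dispensing may be delayed by a time the documents do not allow us to state. An on-site urine test would avoid most of that delay, but the protocol does not now specify one, so it would have to be written in. The fix leaves the gap of up to 4 weeks between screening and the first dispensing as it is.
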